Toxicology: Urine toxicology tests (American Bio Medica Corporation RapidTox Point of Care (POC) test) will be performed at research visits 1, 2, 3, 4, 5, 7, 9, 11, 13, 15, and 17. At these research visits, the RA will ask subjects to provide a urine specimen, unobserved, in a private bathroom. Collection containers and biohazard bags will be available to the study staff from the commercial laboratory. Specimens will be labeled with the name of the research study, the date and time of collection, and the specimen number; no names or other identifying information will be used. The specimen number will be generated using the subject's study ID number, the letters UT (to denote urine toxicology test), and the visit number. The RA will perform the point of care test (results back in 5 minutes). Urine will be tested for multiple substances: amphetamines, barbiturate, benzodiazepine, buprenorphine, cocaine, marijuana, methadone, methamphetamine, opiates, and oxycodone. Results will be recorded in REDCap. Urine toxicology results are confidential and will only be used for study purposes, not recorded in the participant's clinical record.

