### Statistical Model

Multivariable logistic regressions will be applied to test the overall effectiveness of mDOT or PN on the five binary outcomes (success vs. failure) with the SVR rate as the primary outcome. The arm indicator will be the predictor for each outcome. With respect to adherence outcome in particular, repeatedly measured adherence will be analyzed (using 6 post-baseline time points and adherence as a continuous measure) applying a mixed effects linear model to test if the two arms are significantly different. This model accounts for within-subject longitudinal outcome correlation by taking the subject-level intercept as random. All models will include potential confounding variables that are significantly different between the two arms; the sites will be included as a covariate as well. Likewise, mixed effects logistic regression will also be applied to test the significance of PN and DOT on repeatedly-measured undetectable HCV VL throughout the intervention period, adjusting for substance use in addition to other confounding variables. Changes in illicit drug use will be analyzed using urine toxicology data from each visit, counting the “person-month” as a unit of analysis, and analyzing the percentage of person-months that are positive for use of illicit drugs during the study period using a t-test or Mann-Whitney test.

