### **Subgroup Heterogeneity Analyses**

To assess heterogeneity of mDOT or PN effects, additional analyses will be conducted to evaluate whether the mDOT effect varies by variety of subgroups stratified by the following characteristics: OTP (50%) vs. CHC (50%); Males (70%) vs. Females (30%); Patients using illicit drugs during treatment (65%) vs. those not using illicit drugs (35%); HIV/HCV coinfected (28%) vs. HCV mono-infected (72%); Cirrhosis (21%) vs. non-cirrhosis (79%); African American / Latino (41%) vs. Caucasian (59%); Marginally housed (26%) vs. stably housed (74%); Comorbid mental illness (55%) vs. no mental illness (45%); and Peer-support (70%) vs. no peer-support (30%). Initially, subgroups will be defined based on the above factors and estimates of treatment effect will be obtained separately in each subgroup using the methods described above. The significance of any heterogeneous mDOT or PN effects across these factors will be formally tested by testing significance of corresponding interaction terms with the mDOT or PN arm indicator. In addition, we will also conduct within-arm subgroup analyses to identify factors that are associated with outcomes within arms. For example, one test would be if increased social support will be associated with higher treatment initiation within the PN arm.

**Power analysis for subgroup analysis:** For the subgroup analysis, the minimally detectable effect size will depend on the sample size of subgroups. However, assuming that a subgroup has 50% of the total sample, i.e., N=270, and that a base outcome rate is 80% (e.g., SVR), then  $\geq 12\%$  difference will be detected using a Chi-square test. The minimally detectable standardized effect size for continuous outcome will be 0.3. This power analysis also applies to detect binary or continuous factors associated with outcome from within-arm subgroups analyses since the sample size of each arm will be N=270 after attritions. For the subgroups with smaller sample size, the minimally detectable effects sizes, binary or continuous, will be larger. For example, for some of our subgroups will be as small as 20% (or, N= 108) of the sample (e.g. HIV/HCV coinfected), minimum effect sizes are larger at  $\geq 17\%$  for SVR and 0.5 standardized effect size for continuous variables.

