## 4 Preliminary Data Analysis of Baseline Characteristics

### 4.1 Baseline Characteristics

We will consider the following baseline characteristic to characterize the HERO study participants [To be further determined]:

- Demographic Characteristics: Gender, Ethnicity, Race, Age, Education, Marital/ Cohabitation status, Potential Transportation Barrier, Housing status, Employment Status
- Clinical Characteristics: Clinical Setting (OTP or CHC), Cirrhosis, Anxiety Symptoms, Depression Symptoms, HIV/HCV coinfection, HCV-treatment history (Naïve or Experienced), HCV-related information (Genotype, HCV Viral Load), Other infectious

Diseases (HV, HBV, HAV), Medication for Opioid Use Disorder (buprenorphine, methadone)

- Behavior Characteristics: Hazardous alcohol drinking, Injection behaviors (duration, frequency, last drug injection), Substances injected (mixture of heroin and cocaine, mixture of methamphetamine and heroin, cocaine, methamphetamine, heroin, crack, fentanyl), Used drug type (amphetamine, benzodiazepine, , cocaine, opiate, methamphetamine, oxycodone, cannabis/THC)

Detailed information on the baseline characteristics including their definitions and classifications along with all data sources for each characteristic are displayed in Table 1. Briefly, for the baseline demographic factors, the data collected at enrollment visit (consent and demographic survey) will serve as the primary data sources. Data from the screening will serve as the secondary data sources. For the other clinical factors, the data at the screening (chart review 1), enrollment (Chart review 2), or baseline will serve as the primary data sources. If the data are not available at the primary sources, they will be replaced by the secondary data such as the Visit 1/Baseline (chart review 2) research visit data. For the behavior characteristics, the data at the screening or baseline will be used as the primary and only data sources. In short, the data collected at three different time point—screening, enrollment, and baseline/V1 visit (2 week period)—will serve as the primary, or secondary data sources depending on baseline characteristics in effort to minimize missing values.

Table 1. Baseline characteristics

Characteristic	Category	DOT (N=375)	PN (N=379)	Primary source	Secondary source
Gender 				E	S
	Female				
	Male				
	Transgender or Gender Non-conforming				
Age 				E	S
	Mean (SD)				
	Median (Q1, Q3)				

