Last drug injection (within 3 months from screening) 				S	
0-4 weeks					
5-8 weeks					
9-12 weeks					
Number of days injected drugs in the past 3 months 				B	
	Mean (SD)				
	Median (Q1, Q3)				
	Missing				
Times injecting drugs a day 				B	
	Mean (SD)				
	Median (Q1, Q3)				
	<3				
	≥3				
	missing				
Substances injected in the past 3 months 				B	
	Mixture of cocaine and heroin ^				

Characteristic	Category	DOT (N=375)	PN (N=379)	Primary source	Secondary source
	Mixture of methamphetamine and heroinB				
	HeroinC				
	MethamphetamineD				
	CocaineE				
	CrackF				
	FentanylG				
	Poly-substancesH				
Urine drug screen positive at baseline visit 				B	
	Amphetamine				
	Methamphetamine				
	Benzodiazepine				
	Cocaine				
	THC/Cannabis				
	Opiate				
	Oxycodone				
	Any drug				

Notes: S: Screening; E: Enrollment; B: Baseline; CR1 Chart review 1

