### 6.1 Subgroups to be compared

The primary subgroups and their levels are as follows:

- Demographic factors:
  - Sex: Males vs. Females
  - Age: <30 vs.  $\geq 30$
  - Race/Ethnicity: African American vs other; White vs. Other
  - Ethnicity: Latino (Yes vs. No)
  - Employment: Employed vs. Unemployed
  - Education:  $\leq$ HS diploma vs  $>$ HS diploma

- Married/Co-habitating vs. Other
- Housing: Unstable vs. stable
- Ability of transportation vs. Inability
- Clinical factors:
  - Opioid agonist treatment (OAT) clinic vs. community health clinic (CHC)
  - Any medication for OUD in the past 3 months: methadone/buprenorphine vs. none
  - HIV Co-Infection (yes vs. no)
  - HIV viral load: <200copies/mL vs. ≥200copies/mL
  - HCV Genotype (3 vs other)
  - HBV Co-infection: yes vs. no (+ vs. -)
  - Cirrhosis (yes vs. no)
  - Depression (severe/moderate vs. mild/none)
  - Anxiety (severe/moderate vs. mild/none)
  - HCV Treatment naïve vs. experienced
- Alcohol and Drug use:
  - Hazardous alcohol at baseline (yes vs. no)
  - Hazardous alcohol during treatment (yes vs. no)
  - Amphetamine at baseline (UTOX): Yes vs. No
  - Amphetamine during treatment (UTOX): Yes vs. No
  - Benzodiazepine at baseline (UTOX): Yes vs. No
  - Benzodiazepine during treatment (UTOX): Yes vs. No
  - Cocaine at baseline (UTOX): Yes vs. No
  - Cocaine during treatment (UTOX): Yes vs. No
  - THC/Cannabis at baseline (UTOX): Yes vs. No
  - THC/Cannabis during treatment (UTOX): Yes vs. No
  - Opiate at baseline (UTOX): Yes vs. No
  - Opiate during treatment (UTOX): Yes vs. No

- Oxycodone at baseline (UTOX): Yes vs. No
- Oxycodone during treatment (UTOX): Yes vs. No
- Any drug screen + at baseline (UTOX): Yes vs. No
- Any drug screen + during treatment (UTOX): Yes vs. No
- Injecting Behaviors:
  - Last drug injection at baseline: within 5-8 weeks vs 0-4 weeks
  - Last drug injection at baseline: within 9-12 weeks vs 0-4 weeks
  - Times IDU a day at baseline ( $\geq 2$  VS  $<2$ )
  - Times IDU a day during treatment ( $\geq 2$  VS  $<2$ )
  - Times IDU a day at baseline ( $\geq 3$  VS  $<3$ )
  - Times IDU a day during treatment ( $\geq 3$  VS  $<3$ )

Note: Additional subgroup analyses will be conducted based on investigator-driven proposals on concept sheets

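### Illicit drug use is judged by a urine panel that does not list fentanyl, so fentanyl-only users may count as drug-negative in secondary analyses

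*Protocol*

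**What the plan says.** **What urine can show.** Protocol 7.2 (Toxicology) describes a point-of-care test with ten named targets: "amphetamines, barbiturate, benzodiazepine, buprenorphine, cocaine, marijuana, methadone, methamphetamine, opiates, and oxycodone". Neither document provides for a fentanyl strip or for confirmatory testing.

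**What participants may inject.** SAP 4.1 lists the injected substances to be described at baseline, among them "mixture of methamphetamine and heroin, cocaine, methamphetamine, heroin, crack, fentanyl". SAP Table 1 has a fentanyl row under "Substances injected in the past 3 months", with the baseline visit as its source. The SAP's separate list of drug types used, which includes "cocaine, opiate, methamphetamine, oxycodone, cannabis/THC", has no fentanyl entry. Nor do the urine-screen rows of Table 1.

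**What the analyses use.** Protocol 11.10 (Statistical Model) states: "Changes in illicit drug use will be analyzed using urine toxicology data from each visit". The measure is the share of positive person-months, compared with a t-test or Mann-Whitney test. SAP 6.1 lists the subgroup "Any drug screen + at baseline (UTOX): Yes vs. No" and a matching one during treatment. Protocol 11.10 (Subgroup Heterogeneity Analyses) expects 65% of patients to use illicit drugs during treatment and 35% not to.

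**What else is collected.** The Modified ASI (drug use) and the behavioral risk assessment (injecting) are given at many of the same visits. Neither document combines them with urine for this outcome or these subgroups.

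**The concern.** The plan recognises fentanyl as a drug in its own right when it describes participants, but has no urine measure of it. A participant who uses only fentanyl could be urine-negative throughout and be read as not using drugs.

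Drug use during treatment is a pre-specified heterogeneity factor, and it bears on the trial's rationale. Protocol 2.2 reports that in an earlier HIV trial active drug use lowered adherence and that directly observed therapy removed this effect. Protocol 2.1 describes payer restrictions tied to drug use. If the comparison group without drug use contains active users, the contrast between users and non-users is diluted, both for SVR itself and for the effect of mDOT versus PN. The protocol's repeated-measures viral-load model also adjusts for substance use without naming the source, so the same gap may enter there.

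**Working it through.** The plan states no figure for this misclassification, so there is none to reproduce. The check compares the lists and then shows how the error would scale.

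**1. Lists side by side.** The urine panel has ten targets and fentanyl is not one of them. The panel names oxycodone, methadone and buprenorphine apart from opiates, and the SAP names fentanyl apart from heroin. The text therefore gives no basis for treating fentanyl as covered by the opiates strip. It does not state the contrary either, so non-detection is an assumption.

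**2. Who is affected.** Only someone who uses fentanyl and is negative on every other analyte counted. Urine is taken at Visits 2, 3 and 4 during treatment. The SAP does not say how these are pooled. If any positive test counts, the person must be negative at all of them.

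**3. Scale.** Inputs: N = 540 treated after attrition (protocol 11.4) and the 65%/35% split (protocol 11.10), taken first as true use. This gives 0.65 × 540 = 351 users and 189 non-users. Let f be the share of users who are missed. It is not in the documents; 2% to 20% is an assumed range.

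- Missed users m = 351f
- Share of the urine-negative group who are users: c = m / (189 + m)
- Apparent user share = 0.65 × (1 − f)

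| f | m | c | Apparent user share |
|---|---|---|---|
| 2% | 7.0 | 7.0/196.0 = 3.6% | 63.7% |
| 5% | 17.6 | 17.6/206.6 = 8.5% | 61.75% |
| 10% | 35.1 | 35.1/224.1 = 15.7% | 58.5% |
| 20% | 70.2 | 70.2/259.2 = 27.1% | 52.0% |

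N cancels in c, so the shares do not depend on 540. If 65% is instead the urine-positive share, m = 351f/(1 − f) and c = m/189, which gives 3.8%, 9.8%, 20.6% and 46.4%.

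**4. Effect on the contrast.** Suppose missed users respond like other users and there are no false positives. The observed rate in the negative group is then (1 − c) × non-user rate + c × user rate. The observed user minus non-user difference is (1 − c) times the true one. The same holds for the difference in arm effects if c is equal in both arms. This is a risk-difference result; the SAP reports odds ratios, for which it is only a guide. For positive person-months by arm, an equal f tends to dilute the difference, while an f that differs by arm can bias it either way.

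**5. Where self-report is available** (protocol 7.2 and 8.2 to 8.6):

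| Urine visits | Modified ASI | Behavioral risk assessment |
|---|---|---|
| 1, 2, 4, 5, 9, 13, 17 | yes | yes |
| 3 | yes | no |
| 7, 11, 15 | no | yes |

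Every urine visit has at least one self-report instrument, and seven of the eleven have both.

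**The case against.** **Self-reported injecting is already analysed.** SAP 6.1 includes subgroups for last injection (5-8 or 9-12 weeks versus 0-4) and for times injecting per day (cut at 2 and at 3, at baseline and during treatment). They do not depend on the substance and enter the same interaction model (SAP 6.2.2). SAP 6.1 also allows further subgroups by concept sheet. A reader might infer that the plan ignores self-report altogether; the documents do not support that. These subgroups do partly cover active injecting. They compare recency or frequency, however, and do not separate any use from none, so they do not repair the any-drug variable.

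**The SAP label is literal.** It says screen-positive, not user, and the protocol's 65%/35% subgroup does not say that it is defined by urine. The footnote to the any-drug row of Table 1 is not in the text supplied. This stands as a limit on the arithmetic. The risk that readers take urine-negative to mean no drug use remains.

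**The size is unknown.** This stands. The strip's response and f are both assumptions, and pooling several visits and analytes favours small values.

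**Clustering and trends.** A reader might infer that the error concentrates in certain cities or periods, or that a move from heroin to fentanyl would look like falling drug use. The documents give no fentanyl prevalence by site or over time; fentanyl appears only in a list and an empty table. The subgroup models also adjust for site.

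**A combined measure has its own flaw.** The self-report instruments change between visits, so a urine-or-self-report outcome could create a trend by itself. This stands and shapes the fix.

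**Conclusion.** The gap is real but limited. As written, the protocol's change-in-drug-use analysis and the SAP's any-drug subgroups can class a fentanyl-only user as drug-negative, and no part of the plan corrects this. The conclusion assumes that the opiates strip does not detect fentanyl.

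If 2% to 20% of users were missed, about 4% to 27% of the urine-negative group would be users, and the risk-difference contrast would shrink by the same share. The low end is more plausible for the during-treatment subgroup. These figures illustrate scale and are not estimates.

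It would be wrong to infer that the primary result is at risk: the SVR comparison by arm does not use these variables. The drug-use outcome is a protocol analysis that the SAP does not carry forward. The point is a worthwhile and inexpensive improvement to secondary analyses.

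**What to change.** - **SAP 6.1, new subgroup.** Add any drug use at baseline and during treatment, defined as urine-positive OR self-reported drug use or injecting (Modified ASI or behavioral risk assessment). Report it beside the urine-only version. State which panel analytes count, since the panel includes methadone and buprenorphine and the urine rows of Table 1 do not.
- **Recall window.** State it. Eligibility requires injecting within 3 months of screening (protocol 5.1), so a 3-month recall at baseline would make nearly everyone a user and leave no comparison group.
- **Labels.** Call the urine-only variables 'positive for a panel drug (fentanyl not tested)'.
- **Fentanyl subgroup.** Add baseline self-reported fentanyl injection, already a row in Table 1.
- **Change over time (protocol 11.10).** Keep urine-only as the main measure. Add the combined measure as a sensitivity analysis limited to Visits 1, 2, 4, 5, 9, 13 and 17, where urine and both instruments are collected, so that changing instruments do not create a trend.

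The cost is SAP wording and a few derived variables from data already collected. The downside is partial reliance on self-report, which is why the urine-only version stays alongside.

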### 7.3 Non-Clinical Evaluations

Participant surveys: At baseline and every research visit, participants will answer surveys administered by the research assistants who will either record the responses directly into the REDCap database or onto a paper form, then entered into the REDCap database after the research visit is finished.

Medical record: HCV viral load will be obtained when possible by chart review. Information on treatment interruptions and discontinuation will be obtained from medical records.

Adherence by electronic monitors (Med-ic®) and self-report:

Adherence to medications dispensed in electronic blister packs will be measured by electronic compliance monitoring for blistered medications with an attached Med-ic® device. Med-ic® is an innovative stick-on paper label for medication blisters that provides a disposable method to measure adherence (117). Med-ic® packages yield 99.6% event accuracy (time of dose removal correctly recorded within  $\pm 2$  minutes). This technology will allow tracking of medication usage from weekly blister packs prepared by the local pharmacists. Blister packs will be pre-fitted with labels and electronic tags.

In the PN arm, subjects will receive their HCV medication from the medical staff, packaged in 7-14 day blister packs, either weekly or every other week (standard), depending upon the determination of the provider after discussion with the participant. Used blister packs will be returned at research visits for downloading adherence data.

In the mDOT arm, subjects (enrolled in the OTP) will take observed doses at the OTP. The date and time of the dose will be recorded in the mDOT log. Seven-day blister packs containing weekend take-home doses (1-2 doses/week) will be provided on either Friday or Saturday. Blister packs will be collected at each research visit.

Subjects (enrolled in the community health center) will be offered mDOT 7 times a week via a smartphone application, miDOT. Alternatively, mDOT will occur 3 times a week at the community health center observed by the clinic/research staff. If the mDOT is administered at the community health center, dosing logs will be maintained by staff. If receiving miDOT (virtual DOT), subjects will be seen once a week in the clinic and receive one observed dose each week – observed by both clinic/research staff and the miDOT application. Subjects will be provided with 7-day blister packs for all of their doses.

Pill counts will also be performed by counting remaining doses in blister packs. Self-reported adherence will be measured using a single-item visual analogue scale (VAS) which has been shown to correlate well with both pill counts and virological outcomes in HIV-infected patients taking HAART [105, 106].

## 8 Study Schedule

Participants will be followed for up to 180 weeks: Up to 8 weeks ( $\pm 4$  weeks) of pre-treatment evaluation, 12 weeks of treatment, 12 weeks of follow-up to determine SVR12, and 144 weeks of follow-up post SVR12 to determine long-term SVR and reinfection.

### 8.1 Screening and Enrollment

#### 8.1.1 Screening

Potential participants will be identified through two possible means: chart reviews of existing patients at the clinics and by community-based outreach and screening. Eligible participants should be enrolled within one month of screening. If enrollment does not occur within one month, eligibility should be reassessed.

##### 8.1.1.a. Screening with Chart Reviews

Prior to conducting chart reviews of existing patients at the OTP and community clinics, sites will obtain a *Waiver of HIPAA authorization for screening/recruitment purposes*. Once this waiver is obtained, charts of potential participants will be reviewed to determine if the patient is eligible for participation.

- The following will be reviewed through Chart Review Part 1:
  - HCV Antibody (ever)
  - HCV viral load (ever)
  - HCV genotype/subtype (ever)
  - AST/ ALT and platelets in the past 12 months (for FIB-4 fibrosis estimation),
  - Imaging if available to rule out hepatocellular carcinoma if the participant has advance cirrhosis/fibrosis (abdominal ultrasound/CT scan with contrast, or MRI with contrast)
  - Confirm that the person has not previously received DAAs
  - **Document Study eligibility on CRF**

If subject is deemed eligible via “Chart Review Part 1”, then “Eligibility Screener” should be conducted.

### 8.1.1.b. Community-Based Screening

Participants may also be recruited through community-based outreach and screening. Potential participants will be identified through an eligibility screening tool. If they meet basic eligibility criteria – e.g. HCV positive, recent injection drug use – determine if they are currently seeing a provider.

- If they have an HCV provider:
  - Get a release of information to contact the provider
  - Obtain clinical records from the provider
  - **Extract data to assess eligibility (same as listed in 8.1.1.a), documenting on Chart Review Part 1.**
  - **Document Study eligibility on CRF**
- If they do not have an HCV provider:
  - Refer to an HCV provider at the community health center or OTP
  - Get a release of information
  - **Once the clinical record has been started, extract data to assess eligibility as listed in 8.1.1.a, documenting on Chart Review Part 1.**
  - **Document Study eligibility on CRF**

